6.3 Baseline Assessments

Baseline is defined as any assessment performed on or before the day of cryoprocedure.

The following baseline assessments will be recorded prior to cryoprocedure:

- Informed Consent
- Inclusion/ Exclusion Criteria
- Demographics (age, gender, race, ethnicity)
- Height, weight, body mass index (BMI)
- American Society of Anesthesiologists (ASA) physical status classification
- Medical history
- Prior medications and therapies
- Smoking history
- Disease and treatment history
- Laboratory tests (hematology, coagulation, chemistry)
- SF-12 quality of life (QoL)
- Lesion assessments by imaging
- Biopsy and pathology (if available)
- Nephrometry score (NS)

Hounsfield units are recorded in the eCRF for each lesion included in the imaging assessments, separately for the following phases:

- Non-contrast
- Arterial Phase
- Venous Phase
- Delayed Phase.

An increase of ≥ 15 units from the non-contrast phase to any of the 3 other phases will be considered, for the purposes of this SAP, to be an area suspicious for lesion recurrence according to Hounsfield units.

The NS uses the R.E.N.A.L. scoring system. It is based on the 5 most reproducible features that characterize the anatomy of a solid renal mass:

- (R)adius (scores tumor size as maximal diameter)
- (E)xophytic/endophytic properties of the lesion
- (N)eckness of the deepest portion of the lesion to the collecting system or renal sinus
- (A)nterior (a)/posterior (p)
- (L)ocation relative to the polar line.

All components except for (A) are scores of 1, 2, or 3. The (A) describes the principal mass location to the coronal plane of the kidney. The suffix 'x' is assigned to the lesion if an anterior or posterior designation is not possible. An additional suffix 'h' is used to designate a hilar location of the lesion (abutting the main renal artery or vein). The total NS is computed as the sum of the R, E, N and L components, and a total NS of 4 to 6 is considered low complexity, 7 to 9 is considered moderate complexity, and 10 to 12 is considered high complexity. The range of complexity of a renal lesion's NS is from the simplest 4a (1+1+1+a+1) to the most complex 12ph (3+3+3+ph+3) (Kutikiv and Uzzo, 2009).

A lesion is considered to have post-cryoablation recurrence with enhancement if the response to the question “What is the status of the lesion?” in the follow-up lesion assessment eCRF page, is “Recurrent” and the response to the question “If Progressing or recurrent, was the lesion identified by contrast enhancement?” is “Yes” in the follow-up lesion assessment eCRF page. This endpoint will be recorded separately for each lesion.

A lesion is considered to have post-cryoablation progression with enhancement if the response to the question “What is the status of the lesion?” in the follow-up lesion assessment eCRF page, is “Progressing” and the response to the question “If Progressing or recurrent, was the lesion identified by contrast enhancement?” is “Yes” in the follow-up lesion assessment eCRF page. This endpoint will be recorded separately for each lesion.

In order to perform a per-patient analysis, for patients with multiple lesions, the lesion with maximum greatest trans-axial diameter will be considered.

6.4.3 Post-cryoablation biopsy

The endpoint of interest to assess post-cryoablation biopsy is the “Yes” or “No” response to the question “Was a biopsy performed on this lesion?” in the follow-up lesion assessment eCRF page. This endpoint will be recorded separately for each lesion.

In order to perform a per-patient analysis, for patients with multiple lesions, the lesion with maximum greatest trans-axial diameter will be considered.

6.4.4 Disease recurrence

Time to recurrence (TTR) is defined as the time from date of cryoprocedure to disease recurrence with enhancement in at least one lesion. A lesion is considered to have disease recurrence if the response to the question “What is the status of the lesion?” in the follow-up lesion assessment eCRF page, is “Recurrent”, and there is a “Yes” response to the related question, “If Progressing or recurrent, was the lesion identified by contrast enhancement?”

6.4.5 Disease-specific survival

Disease-specific survival (DSS) is defined as the time from date of cryoprocedure until date of death due to kidney cancer. Deaths due to kidney cancer will be identified by a manual review, performed by Galil Medical, of the causes of death recorded in the study database.

6.4.6 Overall survival

Overall survival (OS) is defined as the time from date of cryoprocedure until date of death due to any cause.

6.4.7 Quality of Life

The following ten SF-12 scores, which are computed within the eCRF, will be separately analyzed, as change from baseline and by percentage change from baseline:

- General Health (GH)
- Physical Functioning (PF)
- Role Physical (RP)
- Bodily Pain (BP)
- Vitality (VT)
- Social Functioning (SF)
- Mental Health (MH)
- Role Emotional (RE)
- Mental Component Summary (MCS)
- Physical Component Summary (PCS).

6.4.8 Development of metastatic disease

The endpoint of interest to assess the development of metastatic disease is the “Yes” or “No” response to the question “Is there evidence of metastatic disease?” in the follow-up eCRF page. Per the Steering Committee, metastatic disease is limited to metastases to or from the kidney.

6.4.9 Additional efficacy assessments

Lesion status (i.e., responses to the question “What is the status of the lesion?” in the follow-up lesion assessment eCRF page), will be assessed.

6.5 Safety Assessments

6.5.1 Procedural and intra-operative data

The following will be included in the presentation of procedural and intra-operative data:

- Procedure method (i.e., the response to the question “What was the surgical approach?” in the eCRF)
- Surgical approach type
- Type of Galil Medical cryoablation system used (i.e., the response to the field “Type of cryotherapy system used on patient” in the eCRF)
- Method of monitoring used to place cryoablation needles
- Method of monitoring iceball formation
- Completion of cryotherapy
- Who performed the procedure?
- Type of anesthesia used
- Total anesthesia time
- Estimated blood loss during procedure
- Total duration of operation
- Type of hemostatic agents or maneuvers used
- Number of lesions identified at baseline but not treated with cryoablation
- Number of lesions treated with cryoablation
- Number and type of cryosurgery needles used
- Number of freeze and thaw cycles
- Total freeze time over all cycles; i.e., the sum of the times recorded in the eCRF fields: “Duration of active freeze”
- Total thaw time over all cycles; i.e., the sum of the times recorded in the eCRF fields: “Duration of thaw”
- Lowest temperature achieved at end of all freeze cycles, separately for temperature at the center and at the periphery
- Lesion in right or left kidney?
- Hilar clamping performed?
- Method of thaw
- Was embolization performed prior to cryoblation?
- Involvement of the kidney’s collecting system, according to the following fields on the eCRF:
 - Did the iceball appear to touch the collection system?

- Did the iceball appear to involve (engulf) the collection system?
- Was there evidence for new gross hematuria during the course of the procedure potentially due to involvement of the iceball with the collecting system?
- Post-operative hematocrit (HCT)
- Were other surgical procedures performed during the patient's hospital stay?
- Was an extended hospital stay needed due to an adjunct procedure?
- Achievement of technical success at first post-cryoablation imaging assessment

Time from initial diagnosis of the suspicious renal mass to the date of cryoprocedure will be calculated as follows:

Time from diagnosis of suspicious renal mass (in months) =

$$(\text{Date of cryoprocedure} - \text{Date of diagnosis} + 1)/30.4375.$$

Length of hospital stay (in hours) will be computed using the discharge date and time and the admission date and time recorded on the eCRF.

A patient will be considered to have achieved technical success at first post-cryoablation imaging assessment according to the table below. NB: if any one of the three eCRF fields in the table below have missing data then technical success will also be set to missing.

eCRF field: Was cryotherapy completed?	eCRF field: What is the status of this lesion? (at first post- cryoablation imaging assessment)	eCRF field: If progressing or recurrent, was the lesion identified by contrast enhancement? (at first post-cryoablation imaging assessment)	Derivation of technical success (at first post- cryoablation imaging assessment)
“Yes”	“No longer present”, “Smaller”, or “Stable or no change”	This field should not be completed	“Yes”
“Yes”	“Progressing”, or “Recurrent”	“No”	“Yes”
“Yes” or “No”	“Progressing”, or “Recurrent”	“Yes”	“No”

6.5.2 Adverse Events

Intra-operative device complications will be recorded, and whether or not the complication was related to the malfunction of the cryoablation system. Intra-operative patient complications will also be recorded.

All potentially related and directly related cryoablation adverse events (AEs), serious adverse events (SAEs) and unanticipated adverse device effects (UADEs) that occur within 30 days after the cryoablation procedure will be recorded.

The investigators will use the National Cancer Institute (NCI) Common Toxicity Criteria for Adverse Events [CTCAE] (version 3.0) grading system, and also the Clavien classification. AE terms will be selected from a pre-specified code list within the eCRF, and will be auto-coded within the eCRF using the CTCAE Short Term.

The incidence of AEs will be the number of patients who had the AE (counted only once) divided by the number of patients in the analysis population and represented as a percentage.

6.6 Other Variables

6.6.3 Renal function

6.6.3.1 Estimated Glomerular Filtration Rate

The estimated Glomerular Filtration Rate (eGFR) will be calculated within the eCRF using the Modification of Diet in Renal Disease (MDRD) formula. For serum creatinine (sCR) in mg/dL, and age in years:

$$\text{eGFR} = 175 \times \text{sCR}^{-1.154} \times \text{Age}^{-0.203} \times [1.212 \text{ if Black}] \times [0.742 \text{ if Female}].$$

The change from baseline in eGFR will be computed.

6.6.3.2 Chronic Kidney Disease stages

Chronic kidney disease (CKD) stages will be computed from the eGFR values as follows:

- Stage 1: eGFR ≥ 90 mL/min
- Stage 2: eGFR ≥ 60 and < 90 mL/min
- Stage 3A: eGFR ≥ 45 and < 60 mL/min
- Stage 3B: eGFR ≥ 30 and < 45 mL/min
- Stage 4: eGFR ≥ 15 and < 30 mL/min
- Stage 5: eGFR < 15 mL/min

The change from baseline in CKD stages will be computed.

6.6.3.3 Serum creatinine (sCR)

The change from baseline in sCR will be computed.

7 STATISTICAL METHODS

7.1 General Methodology

All statistical tests will be two-sided with a significance level of $\alpha=0.05$, unless specified otherwise, and will be performed using SAS[®] Version 9.4 or later. Data will be summarized

using descriptive statistics (number of patients [n], mean, standard deviation [sd], median, interquartile range, minimum, and maximum) for continuous variables and using frequency and percentage for discrete variables.

Patient listings of all data from the case report forms (eCRF) as well as any derived variables will be presented.

7.2 Adjustments for Covariates

The following covariates will be included, one at a time, in ‘univariable’ Cox regression analysis of time-to-event efficacy endpoints.

- Age (continuous as age*10 to assess 10 year risk)
- Gender
- Race
- Maximum lesion size (≤ 4 cm, > 4 cm) at baseline using the greatest trans-axial diameter
- Number of cryosurgery needles used
- Type of needles used
 - Needles with the cautery feature (IceRod CX, IceFORCE 2.1 CX, IcePearl 2.1 CX) vs other types; a patient is deemed to be in the ‘Needles with the cautery feature’ group if any needle used in that patient was of that type
- Duration (in months) from date of initial diagnosis of the suspicious renal mass to cryoprocedure (continuous variable)
- Baseline eGFR (continuous variable)
- Histological type (conventional renal cell carcinoma [RCC] versus other)
- BMI (continuous variable)
- ASA classification
- NS complexity category at baseline (low, moderate, high) (as defined in Section 6.3)
- Cryoprocedure surgical approach
 - Note: there is only one patient with an open procedure, so only laparoscopic and percutaneous procedures will be included in this analysis
- Prior renal surgery
- Prior abdominal surgery
- Solitary kidney (yes versus no); a patient is considered to have a ‘yes’ for this variable if ‘Nephrectomy’ is selected on the Medical History eCRF page.
- History of hypertension
- History of diabetes
- Use of anticoagulants

All factors in the univariable models with a two-sided p-value < 0.15 will be included in a multivariable analysis to determine the impact of these factors.

The following covariates will be included, one at a time, in ‘univariable’ logistic regression analysis of the occurrence of an adverse event (AE).

- Age (continuous as age*10 to assess 10 year risk)
- Gender
- Race
- Maximum lesion size (≤ 4 cm, > 4 cm) at baseline using the greatest trans-axial diameter
- Number of cryosurgery needles used
- Type of needles used
 - Needles with the cautery feature (IceRod CX, IceFORCE 2.1 CX, IcePearl 2.1 CX) vs other types; a patient is deemed to be in the ‘Needles with the cautery feature’ group if any needle used in that patient was of that type
- Histological type (conventional renal cell carcinoma [RCC] versus other)
- BMI (continuous variable)
- ASA classification
- NS complexity category at baseline (low, moderate, high) (as defined in Section 6.3)
- Cryoprocedure surgical approach
 - Note: there is only one patient with an open procedure, so only laparoscopic and percutaneous procedures will be included in this analysis
- Prior renal surgery
- Prior abdominal surgery
- Solitary kidney (yes versus no); a patient is considered to have a ‘yes’ for this variable if ‘Nephrectomy’ is selected on the Medical History eCRF page.
- Baseline lesion classification (i.e., exophytic, mesophytic, endophytic).
- History of hypertension
- History of diabetes
- Use of anticoagulants

All factors in the univariable model with a two-sided p-value < 0.15 will be included in a multivariable analysis to determine the impact of these factors.

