6.4. Renal Lesion Size

There are no strict exclusion criteria with regard to lesion size. The typical renal lesion suitable for cryoablation is ≤ 4 cm, however, as TRACE is an observational study of the real-world outcomes of cryoablation surgery using Galil Medical products, physicians are to use their training and experience to determine the size of a renal lesion that is appropriate for cryoablation.

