8.4 Demographic and Other Baseline Characteristics

All demographic and baseline summaries will be displayed for the ITT and RCC populations.

Gender, race, ethnicity, will be summarized using counts and percentages. Age (at date of cryoprocedure, computed using the date of birth), height, weight and BMI will be summarized with descriptive statistics (number of patients [n], mean, standard deviation (SD), median, 25th percentile (p25), 75th percentile (p75) minimum (min), and maximum (max)). Age group (≥ 18 to < 65 years, ≥ 65 to < 75 years, and ≥ 75 years) will be summarized using counts and percentages.

The ASA physical status classification will be summarized using counts and percentages. The number and percentage of patients with medical history events will be summarized. Also, the number and percentage of patients with a history of smoking (current smoker, ex-smoker, never been a smoker) will be given.

Disease related baseline characteristics will be summarized using counts and percentages as follows:

- Previous renal surgery
- On dialysis
- Kidney affected
- Index lesion an incidental or symptomatic finding
- Recurrent disease
- Total number of lesions subjected to cryoablation
- Biopsy performed on the lesion to be treated during the cryoprocedure for the study (note: if multiple lesions were treated, each lesion may not have individual biopsy results)
- At least one malignant lesion by frozen section pathology; a response of “Malignant” in the eCRF field of “What is the frozen section pathology result?” will be classed as a “Yes” for this endpoint, and responses of “Benign”, “Not otherwise specified”, or “Not Done” will be classed as a “No”.
- At least one malignant lesion by permanent section pathology; a response of “Malignant” in the eCRF field of “What is the permanent section pathology result?” will be classed as a “Yes” for this endpoint, and responses of “Benign”, “Not otherwise specified”, or “Not Done” will be classed as a “No”.

Maximum lesion size, using the greatest trans-axial diameter, will be summarized with descriptive statistics and also as categories of ≤ 4 cm and > 4 cm. The maximum lesion volume will also be summarized.

The following lab parameters will be summarized with descriptive statistics:

- eGFR
- sCR; will also be summarized separately for patients with a history of hypertension, for patients with a history of diabetes, for patients with a

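### SAP 7.2 enters lesion size in the Cox and logistic models only as ≤4 versus >4 cm, although the diameter in cm is available; under stated assumptions this loses roughly 40% to 78% of the size information

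*SAP*

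**What the plan says.** SAP 7.2 has two lists of candidate covariates, one for Cox regression of the time-to-event endpoints and one for logistic regression of the occurrence of an adverse event. The same size line stands in both: "Maximum lesion size (≤ 4 cm, > 4 cm) at baseline using the greatest trans-axial diameter". No model has a continuous term for diameter or volume.

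Other measurements in these lists are kept continuous: age and BMI in both, and in the Cox list also time from diagnosis and "Baseline eGFR (continuous variable". The SAP gives no reason for cutting size.

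The measurement is available. Protocol 7.1 collects the greatest trans-axial diameter in cm, and SAP 8.4 says: "Maximum lesion size, using the greatest trans-axial diameter, will be summarized with descriptive statistics and also as categories".

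On the size of treated lesions, Protocol 6.4 says "The typical renal lesion suitable for cryoablation is ≤ 4 cm". It also says "There are no strict exclusion criteria with regard to lesion size" and leaves the decision to the physician.

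Each covariate is first tested alone. Those with a two-sided p-value below 0.15 go into a multivariable model (SAP 7.2).

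**The concern.** If lesions of up to 4 cm are typical, most patients probably fall into one group within which the model sees no difference in size. Where risk rises gradually with diameter, a binary term with a small upper group is a weak stand-in for the measurement.

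Two things are at stake:

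- **The screen.** A weaker size term is less likely to reach p<0.15. If it fails, the size covariate drops out of the multivariable model altogether.
- **Adjustment.** Even when the binary term is kept, size variation within each group is not adjusted for. Surgical approach is a covariate in both lists, and outcomes by approach are a secondary objective (SAP 3). If lesion size differs between laparoscopic and percutaneous cases, part of that difference can remain in the adjusted comparison.

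**Working it through.** The documents give no power, event count or efficiency figure for these models, so there is no planned figure to reproduce.

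**Inputs from the documents.** Binary coding at 4 cm and the p<0.15 screen (SAP 7.2); about 250 patients (SAP 4.4).

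**Assumptions.** The share p of patients above 4 cm is not given; I take 5% to 20%. The size distribution is not given; I take normal and right-skewed forms. The effect is taken as linear in cm.

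**Step 1: information kept by the cut.** Relative to a linear term, this is the squared correlation between size X and the indicator X > 4 cm. For normal X it equals φ(z)²/[p(1−p)], where z is the (1−p) quantile of the standard normal:

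- p = 0.05: z = 1.645, φ = 0.1031, 0.1031²/0.0475 = 0.224
- p = 0.10: z = 1.282, φ = 0.1755, 0.1755²/0.09 = 0.342
- p = 0.20: z = 0.842, φ = 0.2800, 0.2800²/0.16 = 0.490

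The skewed cases use the same squared correlation, by simulation with 2,000,000 draws.

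| Share >4 cm | Patients of 250 | Lost, normal | Lost, log-normal (log-SD 0.3 / 0.4 / 0.5) | Lost, gamma (shape 8 / 4) |
|---|---|---|---|---|
| 5% | 12.5 | 77.6% | 65.4 / 61.2 / 57.1% | 68.6 / 64.8% |
| 10% | 25 | 65.8% | 52.9 / 49.3 / 46.3% | 55.6 / 51.8% |
| 20% | 50 | 51.0% | 41.3 / 39.7 / 39.1% | 42.4 / 39.9% |

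The range is 39.1% to 77.6%, or roughly 40% to 78%. If size is log-normal and the effect is linear in log cm, the normal column applies, because log size is then normal. Outside the assumed shares the loss stays material: with half the patients above 4 cm and normal size it is still 36.3%. If the true effect is a step at exactly 4 cm, the binary term loses nothing.

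**Step 2: the screen (illustration only).** Assume 30 events, a hazard ratio of 1.5 per SD of size, and normal size. Counting only the correct direction, the chance of p<0.15 is Φ(√(d × kept) × ln HR − 1.440), with d the number of events.

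- Continuous: √30 × 0.4055 = 2.221; Φ(2.221 − 1.440) = 0.78
- Binary, 20% above: Φ(2.221 × √0.490 − 1.440) = 0.55
- Binary, 10% above: Φ(2.221 × √0.342 − 1.440) = 0.44
- Binary, 5% above: Φ(2.221 × √0.224 − 1.440) = 0.35

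With 15 events the four figures are 0.55, 0.37, 0.30 and 0.24. With 40 events they are 0.87, 0.64, 0.52 and 0.41.

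**Step 3: adjustment.** The squared correlation in step 1 is also the share of size variance that the binary term accounts for. The share lost is therefore the size variance left unadjusted, before other covariates are considered.

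Two other candidates carry size information. The nephrometry complexity category includes a size component, but this is one of four scores of 1 to 3 that are summed and then cut into three bands (SAP 6.3). "Number of cryosurgery needles used" is also listed, and Protocol 2.1 describes matching needle number to the lesion, but it is a treatment choice as well as a marker of size. Both must pass the same p<0.15 screen.

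**The case against.** The case for the plan is reasonable. The 4 cm cut is prespecified, matches the protocol's reference size and is used throughout SAP 8.4, 8.6.4, 8.6.9.1 and 8.8.1. It answers a readable question: do lesions above the typical size do worse? Size is not the only variable cut, since the nephrometry total of 4 to 12 is also reduced to three bands. The models are exploratory, and SAP 4.4 states that the study is not powered for formal analysis. If the truth is a step at 4 cm, the binary term is the better choice. A change now would come after the Steering Committee reviewed draft tables dated 08 May 2018 (SAP 5.2).

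These points stand. They support keeping the split for description and labelling the change openly. They do not support using only the split in the models: where power is limited, giving up information already collected is harder to justify.

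A reader might also infer more than the documents support:

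- **That a fixed half to three quarters of the information is lost.** No share above 4 cm is given. That range needs about 6% to 20% above the cut, normal size and a linear effect.
- **That patients were selected to have lesions of 4 cm or less.** Protocol 6.4 calls that size typical and sets no size criterion.
- **That size is a leading predictor of recurrence or complications.** SAP 7.2 lists it unranked among many covariates.
- **That every other adjusted estimate is confounded by size.** Nephrometry category and needle number carry part of the size information, and confounding needs size to be related to the factor in question.
- **That the loss converts to an effective number of patients out of 250.** Information in a Cox model depends on events, and no event count is given.
- **That the confidence intervals can be compared directly.** A hazard ratio for >4 versus ≤4 cm and one per cm are different quantities.

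**Conclusion.** The point holds in conditional form. Size is modelled only as a binary covariate although the diameter in cm is available, and the cut probably falls in the upper part of the distribution.

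With 5% to 20% of patients above 4 cm and an approximately linear effect, the loss is roughly 40% to 78% of the size information. The share, the distribution and the linearity are assumptions, and the loss is nil for a true step at 4 cm.

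The consequences are a lower chance of passing the p<0.15 screen and residual confounding by size in the multivariable models, only partly offset by nephrometry category and needle number. Because the models are exploratory, no confirmatory conclusion is affected. This should be changed, but it is not a critical defect.

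**What to change.** - In both covariate lists of SAP 7.2, enter the greatest trans-axial diameter as a continuous variable, per 1 cm.
- Add a simple check for non-linearity, such as a quadratic term or a spline, only if the number of events allows.
- Keep ≤4/>4 cm for the descriptive tables and subgroups.
- Report the models with the binary term as a sensitivity analysis.
- Record the change in SAP 5.2 as made after review of draft tables.

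The cost is SAP wording and the programming for one recoded variable and the extra model runs. No new data are needed. The linear term assumes a roughly linear effect, and the check spends degrees of freedom, which is why it depends on the event count.

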6.2. Inclusion Criteria

Patients are required to meet all of the following criteria to be eligible for participation in the registry:

1. Patient is at least 18 years of age.
2. Patient has a renal lesion suspicious for malignancy.
3. Patient is to undergo renal lesion cryoablation via a Galil Medical cryoablation system using Galil Medical needles for treatment of primary or recurrent disease.
4. Patient is to be available for long-term follow-up per the enrolling physician's standard care practices.
5. Patient has provided written informed consent.

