7.5 Multiple Comparisons/Multiplicity

Since this is a single arm registry study, no adjustment for multiple testing will be performed.

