8.3 Analysis Populations

8.3.1 Intent To Treat (ITT) Population

All patients where a cryoprocedure was attempted with a Galil Medical Cryoablation System and needles and who met the study eligibility criteria will form the Intent-to-Treat (ITT) population. This population will be used for the analysis of all efficacy and safety data. Patients in the ITT population will be identified as follows:

- 1) First include all patients with a date of cryotherapy recorded
- 2) Then exclude any patients who have been manually identified as having not met all eligibility criteria from a review of monitoring reports.

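### In the ITT Cox models for time to recurrence and disease-specific survival, the histology covariate can mix a malignant-versus-benign difference into what looks like an RCC subtype effect

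*SAP*

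**What the plan says.** SAP 7.2 introduces the time-to-event regressions with "The following covariates will be included, one at a time, in ‘univariable’ Cox regression analysis of time-to-event efficacy endpoints". One of the 19 listed covariates is "Histological type (conventional renal cell carcinoma [RCC] versus other"; the same factor is in the list for the adverse-event logistic models. The selection rule is "All factors in the univariable models with a two-sided p-value < 0.15 will be included in a multivariable analysis". No adjustment is made for multiplicity (SAP 7.5: "no adjustment for multiple testing will be performed").

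SAP 7.2, the time-to-event section (8.6.6) and the programming appendix (11.2) do not name the population for these models. Of the ITT set, SAP 8.3.1 says: "This population will be used for the analysis of all efficacy and safety data". That set is defined as "All patients where a cryoprocedure was attempted with a Galil Medical Cryoablation System and needles and who met the study eligibility criteria", and on pathology the eligibility criterion is only "Patient has a renal lesion suspicious for malignancy" (Protocol 6.2). Protocol 7.1 collects pre-procedure biopsy and pathology only where available. SAP 8.4 lists Benign, Not otherwise specified and Not Done among the possible pathology responses and counts all three as not malignant.

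SAP 8.3.2 defines a second population of patients with biopsy-proven RCC (conventional, papillary, chromophobe, collecting duct or unclassified) and assigns efficacy and adverse-event data to it as well. SAP 7.3 leaves missing data to Section 8, which does not mention missing histology.

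**The concern.** ITT patients need not have RCC. With a two-level factor, everyone in the model who is not conventional RCC falls in the second level: four other RCC classes, benign lesions and, depending on the programmer, patients with no usable pathology. Time to recurrence and disease-specific survival are cancer-driven endpoints, so benign lesions may well have fewer events. The second level would then have a lower average hazard even if all RCC subtypes behaved identically.

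Two things are at stake. A hazard ratio above 1 could be read as conventional RCC doing worse than other RCC, which this contrast cannot show. The factor could also enter the multivariable model because of the benign patients. Separately, two programmers could code patients without pathology differently and both comply with the SAP.

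**Working it through.** The documents give no histology mix, recurrence rate, event count or power calculation, so there is no stated figure to reproduce. What follows is a check of the mechanism under stated assumptions.

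**Inputs from the documents.** About 250 patients (SAP 4.4); 5 years of planned follow-up (SAP 4.1); screen at two-sided p<0.15 (SAP 7.2); significance level 0.05, two-sided (SAP 7.1).

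**Assumptions.** ITT shares: conventional RCC 40–60%, other RCC (*non*) 20–30%, benign (*ben*) 10–40%. Five-year RCC recurrence: 5, 10 or 15%. One common hazard for all RCC subtypes. Benign hazard = *b* times the RCC hazard, with *b* = 0, 0.5 or 1.

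**Apparent hazard ratio, conventional versus the second level.** HR = (non + ben) / (non + b × ben). The true subtype hazard ratio is 1.0 throughout.

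| Conventional / other RCC / benign (%) | b = 0 | b = 0.5 | b = 1 |
|---|---|---|---|
| 60/30/10 | 0.40/0.30 = 1.33 | 0.40/0.35 = 1.14 | 1.0 |
| 60/25/15 | 0.40/0.25 = 1.60 | 0.40/0.325 = 1.23 | 1.0 |
| 50/25/25 | 0.50/0.25 = 2.00 | 0.50/0.375 = 1.33 | 1.0 |
| 50/20/30 | 0.50/0.20 = 2.50 | 0.50/0.35 = 1.43 | 1.0 |
| 40/20/40 | 0.60/0.20 = 3.00 | 0.60/0.40 = 1.50 | 1.0 |

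**Undiagnosed patients placed in the second level.** These dilute the distortion, because many of them have RCC. Take 10% recurrence in RCC, none in benign lesions, and a mix of 60% conventional, 15% other RCC, 15% benign and 10% undiagnosed. The RCC share among the diagnosed is 75/90. The second-level rate is 0.10 × (15 + 10 × 75/90)/40 = 5.83%, and HR = ln(0.90)/ln(0.9417) = 1.75. Leaving the undiagnosed out gives a rate of 0.10 × 15/30 = 5.0% and HR = ln(0.90)/ln(0.95) = 2.05.

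**Chance of passing the screen.** The Schoenfeld approximation uses z = |ln HR| × √(D × p × (1 − p)), where D is the number of events and p the conventional share. For 50/25/25, b = 0 and 10% recurrence, D = 250 × 0.75 × 0.10 = 18.75 and z = 0.693 × √(18.75 × 0.25) = 1.50, against a critical value of 1.44 for p<0.15. The chance of p<0.15 is 53%. At 5% and 15% recurrence it is 36% and 66%. A log-rank simulation (250 patients, 3,000 runs, assumed staggered censoring from 12 to 60 months) gives lower values because fewer events are seen:

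| Case (5 / 10 / 15% RCC recurrence) | P(p<0.15) | P(p<0.05) |
|---|---|---|
| 50/25/25, b = 0, ITT, simulated | 32 / 45 / 57% | 13 / 25 / 36% |
| 60/30/10, b = 0, ITT, simulated | 19 to 23% | 6 to 9% |
| 50/25/25, b = 0.5, ITT, Schoenfeld | 20 / 24 / 28% | 8 / 10 / 13% |
| 50/25/25, b = 1, ITT, simulated | 15 to 16% | 5 to 6% |
| RCC patients only, all simulated cases | 14 to 16% | 4 to 6% |

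Restricting the contrast to RCC returns the hazard ratio to 1.0 and the selection rate to nominal.

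**Other endpoints (50/25/25 mix).** If mortality does not differ by benign status, the overall-survival hazard ratio is 1.0. If adverse-event rates do not differ, the odds ratio is 1.0. The documents give no reason to expect a difference in either.

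**The case against.** The strongest reply concerns the endpoint. Under SAP 6.4.4 a recurrence event is a lesion status of recurrent with contrast enhancement, judged locally, with no pathology condition. A benign treated lesion could be recorded that way. A reader might infer that the hazard ratio is inflated by construction. For time to recurrence the documents do not support that: zero benign events is the extreme case, and at equal hazard nothing is distorted. For disease-specific survival (death from kidney cancer, SAP 6.4.5), zero is close to definitional, but no selection rate was computed for it.

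Other points also stand. The label does not say 'other RCC', and a malignant-versus-benign difference would be real; the error lies in reading it as a subtype effect. The contrast is already clean in the RCC population. With a 10% benign share the screen is passed only slightly more often than nominal. The factor is one of 19 in a registry that SAP 4.4 says is not powered for formal analysis, and no Kaplan-Meier estimate depends on it.

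What the reply does not remove is that SAP 8.3.1 applies ITT to all efficacy data, and SAP 7.2 neither moves the histology contrast to the RCC population nor says who belongs in its second level.

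**Conclusion.** The concern holds, conditionally, for time to recurrence and disease-specific survival in ITT. If benign lesions have a lower event rate than RCC, the coded contrast can give a hazard ratio above 1 with no subtype effect. The range is 1.33 to 3.0 under the assumed mixes with no benign events. For the 50/25/25 mix it is 1.33 at half the RCC hazard and 1.0 at equal hazard. The chance of passing the p<0.15 screen ranges from nominal to well above it (32–57% in simulation for 50/25/25 with no benign events). All of this rests on assumed mixes and event rates, so the actual size in this registry is unknown.

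A reader might extend the point to overall survival or the adverse-event logistic models. The documents do not support that: they give no reason why all-cause mortality, or procedure-related events within 30 days, should differ by benign status. For those models only the undefined coding remains open.

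**What to change.** In SAP 7.2:

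- Estimate conventional versus other RCC only in the biopsy-proven RCC population (SAP 8.3.2), with a stated rule for the unclassified RCC response.
- In ITT models, code histology at three levels: RCC, benign, and undetermined or no pathology (including Not otherwise specified and Not Done). Interpret it as malignant versus benign, not as subtype.
- Name the population for each regression.
- Use the same coding in the adverse-event logistic models, for consistency only.

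The cost is a few sentences and one recoded variable, built from pathology responses already on the eCRF, plus one extra degree of freedom in the ITT models. One downside needs a rule in advance: if the benign level has no events, its Cox hazard ratio is not estimable. Report that level descriptively, or use Firth's penalised likelihood.
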